# **Transcranial Photobiomodulation for reducing autism symptoms in children.**

*May 1, 2022*

PROTOCOL TITLE:

Transcranial photobiomodulation for reducing autism symptoms in children.

PRINCIPAL INVESTIGATOR:

Name	[name]
Department	N/A
[contact]

RESEARCHERS:

Name	[name]
Department	N/A
[contact]

Name	[name], CFA, Esq.
Department	N/A
[contact]

Name	[name]
Department	N/A
[contact]

1.0 Purpose of the study:

The purpose of this 10-week feasibility study is to assess the tolerability, safety and efficacy of Transcranial LED Therapy for language learning and reducing symptoms of autism in children.

The investigators propose to enroll up to 30 participants, 2-7 years old, all of whom have recently completed the IRB approved study by JelikaLIt. They all have been previously diagnosed with moderate to severe ASD by licensed professionals according to the Diagnostic and Statistical Manual of Mental Disorders, Fifth Edition (DSM-5) criteria for Autism Spectrum Disorder (ASD).

This will be an one-arm, open label study. Participants who were in the placebo condition in the previous study, will receive the treatment. Participants who were in the active condition in the previous study will repeat the course of treatment after the intermission of 3-6 months (depending on when they completed the study).

The hypothesis to be tested is that exposure to photobiomodulation will reduce children's symptoms of autism, as measured by the reduction of the Mean Scores of the Childhood Autism Rating Scales, compared to the initial baseline.

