## 2.4 Results of the Previous Pilot Study using the same device

[figure not shown]
Our recently concluded pilot study collaborates these predictions. We enrolled 30 participants who were 2-6 year old (16 in active and 14 in sham-control condition). Participants in the active condition have improved significantly (as measured by Childhood Autism Rating Scale). Participants in the sham condition showed no such improvement (see Chart 1). Furthermore, EEG data showed reduction of Delta waves over the course of the study for the participants of Active condition only (see Chart 2). Frolich et al (2021) reported that high amplitude Delta waves in the wakeful state are associated with neurological disorders and mitochondria disorders. Therefore, this reduction of Delta waves is a signature of the brain healing process (see attached presentation by Naviaux, 2021). Lastly, the change in Delta correlated significantly with the change in CARS showing that the kids whose CARS scores reduced (reflecting their reduction of symptoms) also experienced reduction in their Delta waves (see Chart 3). Lastly, we also found an increase in Theta waves in the children, whose CARS score decreased (inverse correlation between intensity of Theta and CARS scores, see Chart 4). Recent research has shown that there is an insufficient intensity of Theta waves in the children diagnosed of ASD (e.g., Ortiz-Mantilla et al, 2019). This redistribution of brain waves from Delta to Theta in the active condition is signaling of the healing that's happening as a result of treatment with tPBM.

(See attached Charts 1-4 with exact statistics below).

[figure not shown]
**Chart 1:** There was a significant reduction in CARS score in the Active Condition only ( $F=6.47$ ,  $p<.05$ ).

[figure not shown]
**Chart 2:** Delta Waves reduced in the Active Condition: Pearson's R squared  $-.45$ , ( $p<.05$ ,  $n=9$ ) However, this correlation was not significant for the Placebo Condition, Pearson's R squared is  $-.1$ , ( $p>.1$ ,  $n=8$ ).

**Chart 3:** The study revealed a statistically significant correlation between the change in CARSII scores and Change in Delta waves (n=15). Specifically, children (mostly in Active condition), who experienced reduction in CARSII also experienced reduction in Delta waves.

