**7.0 Procedures Involved:**

7.1 Location: The study will use pre-test and post-test design. The entire study on the children will be done in the office. The weekly interview with the parent may be done either in office or by phone, as preferred by the parent.

7.2 Conditions: There will be only one active condition.

7.3 Participants: The participants will be 2 to 7 years old children previously diagnosed with moderate or severe ASD. Children of all genders and races will be included in this study.

7.4 Treatment: The treatment will take place twice a week for up to 30 minutes at a time.

During the study, while participants will be wearing the photobiomodulation device, they may be playing with their parent or the experimenter, using the toys of their choice (out of the many available in the experimenter's office). The caregivers will be present during the experiment at all times. When the child and the parent arrive, they will be welcomed to the office, and introduced to the toys.

The child will be encouraged to play with toys and interact with the parent (or the experimenter).

If the child becomes uncomfortable, the parents will be able to leave the experiment without any punishment. No coercion or deception is involved in this study.

7.5 Pre and Post-Testing:

The following measurements will be used for pretest and post-test.

- Childhood Autism Rating Scale (CARS2)

CARS 2 scores will be compared for analyses.

In addition, EEG will be collected from the participants pre and post -treatment in each session. Mobile FDA cleared EEG device from Brain Scientific will be used to collect children's pre and post test EEG.

There is no known danger of EEG collecting. In this study it will be using for measuring the efficacy treatment only.

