**7.6 On-going Data Collection:** Parents will be asked to keep a daily diary of the child's behavior, specifically – words spoken, comprehension of instructions, eye contact, his sleep pattern, number of tantrums, anxiety, social interaction and eating. Qualitative data will be collected through short weekly interviews with the parents. These interviews can take place either in [name] office during the child's treatment or by phone. During those weekly interviews, the parents will be asked questions about their children's responsiveness to language, number of words they can produce, eye-contact, anxiety, frequency of tantrums, eating, and difficulties falling asleep and sleeping through the night. Please see attached proposed script for the weekly call. The qualitative data will be used to further inform and supplement quantitative data.

The study will collect qualitative and quantitative data. The quantitative data will be the total CARS2 scores of the participants, obtained before and after the study is done. Repeated-measure t-tests will be used to analyze quantitative data. In addition, we will collect Before and After Prefrontal cortex EEG from the control and experimental treatment groups to measure electrophysiological changes in Prefrontal cortex. after treatment. EEG data will be analyzed (using Time-Frequency analysis), and after baseline normalization, the data will be used in aggregate to compare conditions numerically. In addition, we will obtain qualitative data from weekly parental interviews, during which we will ask participants' parents about their children's behavior (see attached protocol). Qualitative data will be used for information purposes and will supplement quantitative data.

The PI will analyze quantitative and qualitative data. An independent contractor (a neuroscientist) will be analyzing the collected EEG data at the end of the study, however, the individuals conducting the analysis will not have access to the private identifiable information.

**7.8 Confidentiality:** Participants' confidentiality will be protected by assigning them Study ID. The quantitative data will be analyzed and reported only as aggregate (averages and F scores). The qualitative data will be studied only by the researchers and, if reported for illustrative purposes only, it will be attached to the Study ID (not the identifying information). The participants will be asked for consent to report qualitative data with the Study ID.

●

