# Data Collection and Statistical Analysis

## Primary Analyses

The last author, a licensed psychologist experienced in the use of CARS in clinical practice, conducted blinded Before and After CARS ratings for all participants. The final CARS evaluations were performed immediately after the final treatment session. CARS scores were analyzed using the independent sample t-test. We compared the differences from the baseline between both groups, calculating both the average difference and 95% CI within each group and between groups.

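### The SAP's primary analysis compares Active with Sham under blinded rating, but the protocol's trial has one open-label arm: the two documents describe different designs

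*SAP*

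**What the plan says.** **Protocol.** Section 1.0 fixes the design: "This will be an one-arm, open label study". Children who had placebo before now receive the device, and "Participants who were in the active condition in the previous study will repeat the course of treatment after the intermission of 3-6 months". Section 7.2 agrees: "There will be only one active condition". The hypothesis in section 1.0 is a reduction in symptoms "as measured by the reduction of the Mean Scores of the Childhood Autism Rating Scales, compared to the initial baseline". Section 7.6 names the data and the test: "The quantitative data will be the total CARS2 scores of the participants, obtained before and after the study is done", and "Repeated-measure t-tests will be used to analyze quantitative data".

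**SAP.** Under Primary Analyses, a psychologist rated every child blinded, before and after, and "CARS scores were analyzed using the independent sample t-test". Changes from baseline were compared between two groups, with mean differences and 95% CIs both within and between groups. Under Primary Outcome the SAP gives:
- Active (n = 16): mean 43.5 before, 33.7 after.
- Sham (n = 14): mean 40.6 before, 38.0 after.
- Difference in change: 7.23 (95% CI 2.357 to 12.107, p = 0.01).
- Reduction of at least 4.5 points: 14 Active and 5 Sham children, reported as a significant difference and followed by the efficacy conclusion.

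**The earlier study.** Protocol section 2.4 describes a completed sham-controlled pilot of 30 children: "16 in active and 14 in sham-control condition". Section 5.0 says the present trial expects to bring those children back.

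**The concern.** The primary analysis in the SAP needs two concurrent groups, one of them on sham. The protocol's trial has one group, all treated and unblinded. The SAP is also written in the past tense, as finished results. If it is taken as the plan for this trial, its main test cannot be run. If its numbers are taken as this trial's results, a controlled treatment effect and an efficacy claim become attached to a study with no control. On the SAP's own figures 5 of 14 Sham children reached the 4.5-point reduction, so improvement without active treatment is not negligible. A single arm cannot separate that improvement from an effect of the device.

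**Working it through.** **1. Reproduce the SAP's figure.** Inputs: the means, group sizes and CI under SAP, Primary Outcome.
- Active change: 43.5 - 33.7 = 9.8.
- Sham change: 40.6 - 38.0 = 2.6.
- Difference: 9.8 - 2.6 = 7.2, against 7.23 stated; the gap is rounding of the means.
- CI midpoint: (2.357 + 12.107)/2 = 7.232. Half-width: (12.107 - 2.357)/2 = 4.875.
- Assuming a pooled two-sample t-test, df = 16 + 14 - 2 = 28 and t(28, 0.975) = 2.048. SE = 4.875/2.048 = 2.38.
- t = 7.232/2.38 = 3.04, two-sided p = 0.005, which rounds to the stated 0.01.
- Implied SD of change: 2.38/sqrt(1/16 + 1/14) = 6.50. The stated before and after SDs give a similar SE (2.44) at a before-after correlation of 0.5.

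The figure is therefore internally sound as a two-sample comparison of 16 with 14 children. It is not a paired test on one group.

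**2. Set it against the protocol's design.**

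| Element | Protocol | SAP |
|---|---|---|
| Arms | one, all treated (1.0, 7.2) | Active and Sham |
| Blinding | open label (1.0) | blinded ratings |
| Question | change from baseline (1.0) | difference in change between groups |
| Test | repeated-measure t-test (7.6) | independent-sample t-test |
| Sample | up to 30 in one group (5.0) | 16 versus 14 |

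In the protocol's trial the second term of 9.8 - 2.6 does not exist. A paired test there asks whether one mean change differs from zero, with n - 1 df (29 if all 30 children enrol).

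**3. Sort the SAP's outputs.** The between-group test, its CI and the Active-versus-Sham responder test cannot come from one arm. The within-group mean change with its 95% CI can. A responder count can too, but only as a single-group proportion.

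**4. Test the likely source.** The 16/14 split equals that in Protocol 2.4. The only other CARS statistic given there is F = 6.47 (Chart 1). For two groups measured twice, the group-by-time F equals the square of the t for change; the SAP implies 3.04 squared, about 9.2. The two do not match, but the protocol does not say which effect its F tests. This check neither confirms nor refutes the common source.

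**The case against.** The strongest reply is that nobody chose a two-sample test for a one-arm trial. The SAP text reads like results from a sham-controlled study, where comparing change between groups is an ordinary primary analysis. That stands: a reader might infer a poor choice of test, and the documents do not support it. The fault is a mismatch between documents.

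It follows that the direction of repair should not be assumed. A reader might infer that the SAP certainly reports the earlier study. The group sizes and the returning children make this probable, but the F statistic does not confirm it, and parts of the documents not available here may state the source. The sponsor has to settle this first.

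A reader might also infer that the SAP contains nothing for the protocol's paired analysis. That goes too far. The SAP calls for a within-group mean difference with a 95% CI, which is the estimation side of a paired t-test. Only the test itself is unnamed.

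Two further replies carry less weight:
- The returning children could be compared by former assignment. Both groups would be on active treatment, however, so this would not be Active versus Sham, and neither document plans it.
- The protocol keeps two-arm wording of its own. It promises to control for therapy in control and experimental conditions (4.0, inclusion item 3), to compare EEG between conditions (7.6), to check that parents understand placebo is possible (10.0), and to match children for assignment (14.0). This shows the protocol also needs cleaning. It does not displace the one-arm statements on design, conditions, hypothesis and CARS test.

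**Conclusion.** The concern holds as a contradiction between the documents, and it affects the primary analysis. The 7.23-point difference, its interval, the responder comparison and the efficacy conclusion cannot be results of the one-arm, open-label trial in the protocol, because they depend on a Sham change of 2.6 points that this trial will not observe. The within-group mean change with its 95% CI is the part of the SAP's analysis of means that carries over.

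The contradiction itself rests on no assumption. The recalculated SE and SD assume a pooled t-test and serve only to show that the SAP's figure is a two-sample one. That the SAP reports the earlier study is probable, not established. The documents give no one-arm results and no SD of within-child change, so the size or precision of the paired result cannot be computed from them.

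**What to change.** 1. **Confirm the source first.** The sponsor should state which study the SAP's Primary Analyses, Baseline Data and Primary Outcome text reports. Whatever the answer, SAP and protocol must describe the same design before a primary result is stated.
2. **If it is the earlier study,** label that text as background, and do not present 7.23 or the efficacy conclusion as this trial's result. Write a primary analysis for this trial: within-child change in total CARS2, by paired t-test with 95% CI, as Protocol 7.6 already names. Give any responder result as a single-group proportion. State that change without a concurrent control cannot be attributed to the device.
3. **Clear the two-arm wording from the protocol.** Change the EEG comparison in 7.6 to a within-child before/after comparison. Reconcile inclusion item 3 in 4.0, the placebo wording in 10.0 and the assignment wording in 14.0 with the one-arm design.

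Cost: a short new SAP section and wording corrections in the protocol, with no extra children or data. The downside is a conclusion limited to uncontrolled change from baseline, which is all that a one-arm design supports.

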#### 14.0 Provisions to Protect the Privacy and Confidentiality of Participants and the Research Data:

Participants will be only interacting with [name], [name], Esq, or [name] (researcher). Participants and their parents will be tested individually, in a quiet room, and their confidentiality will be protected, as they won't be interacting with each other or with anybody else outside of the researchers.

The participants will be explained that they can refuse to answer any question. They can also refuse to participate in the study at any time. We do not anticipate uncomfortable questions, however, we will assure the participants that their level of comfort is of utmost importance, and we will explain to them that there is no penalty involved for their refusal to answer any specific question.

Only [name] and [name] will be able to access individual information. The participants will be immediately assigned Study ID number and only STUDY ID will be used for data analysis and reporting. Only aggregated data will be used for further reporting to the scientific community or to the business community. Individual data will be reported for illustrative purposes only with STUDY ID (not identifying personal information).

The following information will be included as data: Signed consent form (immediately scanned and stored in a cloud). Pre and Post-test Cars2 scores (with STUDY ID assigned). Weekly interview data (with STUDY ID assigned).

Identifying information will include Name and Age, Gender and number of therapy hours of the participant, Name and phone number of the parent. Children's age, gender and number of therapy hours will be used for matching purposes (for assigning to the control or treatment condition). Neither names of the participants nor names and phone numbers of their parents will be used for data analysis or reporting. Their names and phone numbers will be stored separately, in encrypted (password protected) file, in a secure cloud. Secure clouds as well as encryption and password protection will be used to protect identifying information.

The raw research data will be stored for 6 years. The identifying parental information will be kept for a year, for potential follow up interviews. The consent form will include their permission to keep identifying data for a year.

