## Outcomes

### Baseline Data

At the beginning of the trial, an initial evaluation was performed to assess the severity of ASD in participants using the CARS score. Table 1 displays the mean, median, and range of the participant scores. Most participants had moderate to severe ASD, with a CARS score higher than 35. There were no significant differences in age, gender, ethnicity, language status, treatment status, or CARS scores between the Active and Sham groups.

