### Primary Outcome

Every participant who completed the trial was evaluated with CARS post-treatment. There were no missing CARS posttreatment evaluations. In the Active group, the before treatment CARS scores had a mean score value of 43.5 (n = 16) with a standard deviation (SD) of 5.7, the after-treatment scores had a mean score of 33.7 with an SD of 5.0. In the Sham group, the before treatment CARS scores had a mean score value of 40.6 (n = 14) with SD of 7.2, the after-treatment scores had a mean score of 38.0 with SD of 8.4. Table 3 shows the mean (M) and SD of the CARS scores for the Active and Sham groups before and after treatment. The difference in the change in CARS between the two groups was 7.23 (95% CI 2.357 to 12.107, p=0.01).

In addition to analyzing the changes in CARS scores based on averages, we also conducted respondents-based analyses, quantifying the number of participants in Active and Sham groups, whose change in CARS was greater than 4.5 points (as it has been suggested by Jurek et al 2022 to be the minimal clinically important difference). The result was significant  $\chi^2=8.48$ ,  $p=.004$ . By the end of the trial, 87% of the participants in the Active group (14) had achieved an equal or greater than 4.5-point reduction in CARS scores, only 35% of the participants of Sham group (5) achieved an equal or greater than 4.5-point reduction in CARS scores. The number of subjects that achieved this minimal clinically important difference in the Active group was statistically significantly higher compared to the Sham group. Therefore, the treatment was considered to have clinically meaningful efficacy.

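### The SAP compares CARS change between Active and Sham with no baseline covariate despite a 2.9-point baseline gap; a baseline-adjusted estimate, roughly 5.9 against 7.23 under stated assumptions, should be reported beside it

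*SAP*

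**What the plan says.** The SAP (Primary Analyses) gives the method as "CARS scores were analyzed using the independent sample t-test" and the quantity compared as "We compared the differences from the baseline between both groups". No covariate is named.

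The SAP (Primary Outcome) supplies the starting points: "In the Active group, the before treatment CARS scores had a mean score value of 43.5 (n = 16", with an SD of 5.7, and "In the Sham group, the before treatment CARS scores had a mean score value of 40.6 (n = 14) with SD of 7.2". Post-treatment means are 33.7 (SD 5.0) in Active and 38.0 (SD 8.4) in Sham. The result is "The difference in the change in CARS between the two groups was 7.23 (95% CI 2.357 to 12.107, p=0.01".

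The SAP (Baseline Data) adds: "There were no significant differences in age, gender, ethnicity, language status, treatment status, or CARS scores between the Active and Sham groups".

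No baseline-adjusted CARS analysis appears in either document. The only adjustment mentioned is for behavioral therapies (Protocol 4.0, inclusion criterion 3). On allocation, the visible text offers only Protocol 14.0, where children's "age, gender and number of therapy hours will be used for matching purposes (for assigning to the control or treatment condition". Baseline CARS is not among those variables.

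**The concern.** Baseline CARS is the pre-treatment measurement of the outcome itself and was already collected. A t-test on change subtracts it with a coefficient of exactly 1. If the true within-arm slope of post-treatment on baseline CARS is below 1, children who start higher tend to fall further whatever they receive, and the arm that starts higher is credited with part of that fall. Active is that arm, by 2.9 points or about 0.45 of a pooled SD.

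Two things are at stake: the size of the reported mean difference, given the imbalance that occurred, and its precision, because a slope forced to 1 leaves more residual variance than a fitted slope.

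**Working it through.** **Inputs** (all from SAP, Primary Outcome)
- Active, n = 16: baseline 43.5 (SD 5.7), post-treatment 33.7 (SD 5.0).
- Sham, n = 14: baseline 40.6 (SD 7.2), post-treatment 38.0 (SD 8.4).
- Difference in change 7.23, 95% CI 2.357 to 12.107, p = 0.01.
- The pre/post correlation is not printed. It is solved for below.

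**1. Reproduce the reported figure.**
- From the means: (43.5 − 33.7) − (40.6 − 38.0) = 9.8 − 2.6 = 7.2. The CI midpoint is 7.232. These agree.
- SE = half-width / t(0.975, 28 df) = 4.875 / 2.048 = 2.380.
- t = 7.232 / 2.380 = 3.04, p = 0.005, which rounds to the printed 0.01.

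**2. Back-solve the slope (equal-variance t-test).**
- Pooled baseline variance = (15 × 5.7² + 13 × 7.2²) / 28 = 41.47.
- Pooled post-treatment variance = (15 × 5.0² + 13 × 8.4²) / 28 = 46.15.
- Variance of change = 2.380² / (1/16 + 1/14) = 42.29.
- Covariance = (41.47 + 46.15 − 42.29) / 2 = 22.67.
- Slope = 22.67 / 41.47 = 0.547 (pre/post correlation about 0.52).
- Residual variance = (46.15 − 22.67² / 41.47) × 28/27 = 35.0.
- SE(slope) = √(35.0 / (28 × 41.47)) = 0.174. With 27 df the 95% CI is 0.19 to 0.90; the test of slope = 1 gives p = 0.015.

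**3. Adjusted difference.**
- (38.0 − 33.7) + 0.547 × 2.9 = 4.3 + 1.59 = 5.89.
- SE = √(35.0 × (1/16 + 1/14 + 2.9² / (28 × 41.47))) = 2.22, against 2.38 unadjusted (7% smaller).
- t = 2.65 on 27 df, p = 0.013, 95% CI 1.3 to 10.4.
- Shift from 7.2: (1 − 0.547) × 2.9 = 1.3 points, about 18%.

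**4. How firm is 5.9?**
- *Uncertainty in the slope.* At 0.19 the reduction is 0.81 × 2.9 = 2.3 points; at 0.90 it is 0.10 × 2.9 = 0.3.
- *Other readings of the printed statistics, common slope kept:*

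| Reading | Slope | Adjusted difference | p |
|---|---|---|---|
| Printed CI, equal-variance | 0.55 | 5.89 (1.3 to 10.4) | 0.013 |
| Printed CI, Welch | 0.52 to 0.66 | 5.82 to 6.20 | 0.016 to 0.005 |
| p = 0.01 taken literally | 0.44 | 5.58 (0.7 to 10.4) | 0.026 |
| F = 6.47 from Protocol 2.4, Chart 1 | 0.33 | 5.25 (0.2 to 10.3) | 0.043 |

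The last row is weak. Chart 1 describes its result as "There was a significant reduction in CARS score in the Active Condition only", and F = 6.47 is not labelled as the between-group test. It also conflicts with the printed CI, which implies t² = 9.2.

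- *Unequal slopes.* The printed figures fix only a weighted sum of the two arms' covariances. The extremes are an Active correlation of 0 (slopes 0 in Active, 0.94 in Sham) and of 1 (slopes 0.88 and 0.31). The difference at the overall mean baseline of 42.15 is then 5.76 or 5.96. At Active's mean it is 7.03 or 5.19; at Sham's mean, 4.30 or 6.84.

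**The case against.** Much of the opposing case stands.

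- **The t-test on change is a valid test.** Under random allocation it is not biased as a method. The point concerns precision and the estimate given the imbalance that occurred.
- **A reader might infer that 5.9 is the correct value and 7.23 an error.** The documents do not support that. No visible passage says allocation was random. The matching sentence in Protocol 14.0 sits in a one-arm protocol and may be carried over from the earlier study. If allocation was not random, the change-score and adjusted estimates answer different questions and neither is automatically right.
- **A reader might take 5.3 to 6.2 (the table in the working) as the full uncertainty.** It covers only readings of the printed figures under a common slope. The slope interval and arm-specific slopes allow more, and one extreme gives 7.0 at Active's mean baseline, close to the reported value. The SE also assumes equal residual variance, although post-treatment SDs are 5.0 and 8.4.
- **A reader might infer that the SAP left out baseline CARS because the groups did not differ significantly.** The SAP gives that sentence as description and never as a reason for the method. Equally, the non-significant gap (t = 1.23, p = 0.23) does not remove the effect of 2.9 points on a change-score estimate.
- **A reader might infer that the efficacy conclusion falls with 7.23.** It does not. That conclusion directly follows the responder contrast (14 of 16 against 5 of 14), which this point leaves untouched.
- **Little changes, and not in the protocol's own study.** True: this concerns the completed Active/Sham comparison that the SAP reports. The protocol's paired one-arm analysis has no between-group baseline gap to adjust for.

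What remains is that a collected covariate closely tied to the outcome was not used, in a sample of 30 with a visible imbalance on it.

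**Conclusion.** The point holds in limited form. The reported mean difference comes from a valid but less efficient analysis, and the SAP's own figures suggest it is larger than a baseline-adjusted estimate would be: about 5.9 (1.3 to 10.4) against 7.23 (2.36 to 12.11), with SE 2.22 against 2.38. This rests on random allocation, a common slope, equal residual variance and a slope back-solved from the printed SDs and CI. Significance at the 5% level and direction survive every reading checked. This is an improvement in the size and precision of one reported estimate and does not overturn the result. The exact adjusted value needs patient-level data.

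**What to change.** 1. Keep the t-test on change as reported.
2. Beside it, report an ANCOVA of post-treatment CARS on group and baseline CARS from patient-level data, with the adjusted difference and 95% CI, labelled post hoc.
3. Fit a group-by-baseline term as a check on the common slope. If the slopes appear to differ, say at which baseline value the difference is quoted.
4. State how the Active and Sham children were allocated (random, matched, or both), so that the adjusted figure can be interpreted.

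The cost is one extra model on existing data, its interaction check, and two sentences. The SAP reports no missing post-treatment CARS among completers, so no new data are needed. The downside for the sponsor is that the mean difference is likely to be somewhat smaller.
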